	
The open-label stabilization phase will start with the baseline visit (Day 1). Doses will be titrated (based on 2 weight groups [< 50 kg or ≥ 50 kg]) during this phase to establish an optimal, stabilized aripiprazole dose for each subject. Dose adjustments are not permitted after the Week 8 visit. Starting at Week 2, subjects meeting the stabilization criteria ($\geq 35\%$ improvement [decrease] of Yale Global Tic Severity Scale [YGTSS] Total Tic Score [TTS]) who demonstrate a continued response as described ($\geq 35\%$ improvement [decrease] of YGTSS TTS) for 12 consecutive weeks, inclusive, with no more than one excursion of response criteria will enter the double-blind randomized withdrawal phase. Stabilization can be achieved by Week 14 at the earliest. Excursions will not be permitted at the end of the 12th consecutive week of stabilization (ie, the randomization visit).
 
Subjects entering the double-blind randomized withdrawal phase will be randomized 1:1:1 to the half-dose aripiprazole arm, full-dose aripiprazole arm, or placebo arm. Randomization will be stratified by region and weight group. Doses in the aripiprazole arms will be based on each subject's stabilized dose from the open-label stabilization phase. Subjects will be monitored for relapse during the double-blind randomized withdrawal phase. Relapse is defined as a loss of $\geq 50\%$ of the improvement experienced during the open-label stabilization phase (ie, improvement at the last assessment of YGTSS before randomization) on the YGTSS TTS.
 
There will also be a safety follow-up period (30 + 3 days) after the last dose of investigational medicinal product (IMP) or after the clinical site is notified that the subject prematurely discontinued their IMP.

Subject Population:
	
The trial population will include pediatric subjects, 6 to 17 years of age, meeting the current Diagnostic and Statistical Manual of Mental Disorders, fifth edition (DSM-5) diagnostic criteria for TD. It is anticipated that approximately 228 subjects will be enrolled in the open-label stabilization phase in order to randomize approximately 114 subjects into the double-blind randomized withdrawal phase.

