3.6 Measures to Minimize/Avoid Bias

3.6.1 Randomization

Subjects will be randomly assigned in a 1:1:1 ratio via interactive response technology (IRT) to the half-dose aripiprazole arm, full-dose aripiprazole arm, or placebo arm. The randomization will be stratified by region and weight group, where region is classified as North America (including USA and Canada) vs. Rest of the World and weight group is classified as low weight (body weight at Baseline < 50 kg) vs. high weight (body weight at Baseline \geq 50 kg). Computer-generated randomization codes will be prepared by a sponsor's independent biostatistician.

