3.7 Trial Procedures

The duration of this trial from first subject enrolled to last subject completed is estimated to be approximately 3 years and 4 months including an estimated 30-month recruitment period.

Individual participation for subjects who complete the trial can range from a minimum of approximately 30 weeks to approximately 42 weeks. Length of participation will vary, depending on the screening duration (3 - 42 days).

Protocol 31-14-204

However, the trial may be terminated early based on the result of a planned interim analysis (IA).

During the open-label stabilization phase, visits will occur at Week 1 (± 2 days) for the titration visit and at Weeks 2, 3, and 4 (± 2 days) and Weeks 6, 8, 10, 12, 14, 16, 18, and 20 (± 3 days). Upon entering the double-blind randomized withdrawal phase, subjects will be randomized to aripiprazole full dose, aripiprazole half dose, or placebo. Subjects will have trial visits at Weeks 1, 2, 3, and 4 (± 2 days) and Weeks 6, 8, 10, and 12 (± 3 days).

Screening assessments may occur during 1 or more visits (as needed), and must occur in the clinic. The baseline visit will occur in the clinic, as well the open-label stabilization phase visits on Weeks 1, 2, 4, 8, 12, 14, 16, 18, and 20 and the double-blind, randomized withdrawal phase visits at Weeks 1, 2, 4, 8, and 12. All other visits will occur via telephone with direct patient visualization (except for open-label Week 3 which does not require direct patient visualization), web, in-clinic, or other acceptable means of contact. Trial assessment time points are summarized by phase in [Table 3.7-1](#) (Pretreatment and Open-label Stabilization Phase) and [Table 3.7-2](#) (Double-blind Randomized Withdrawal Phase).

Protocol 31-14-204

Assessments/Procedures	Screening and Washout Period (Days -42 to -3)	Open-label Stabilization Phase Visits - Week (Day) ^a												
		Baseline (Day 1)	1 (8 ± 2)	2 (15 ± 2)	3 (22 ± 2)	4 (29 ± 2)	6 (43 ± 3)	8 (57 ± 3)	10 (71 ± 3)	12 (85 ± 3)	14 (99 ± 3)	16 (113 ± 3)	18 (127 ± 3)	20 (141 ± 3) / EOP or ET ^b
Screening/Eligibility														
Informed Consent/Assent ^c	X													
Confirmation of diagnosis of TD by DSM-5 ^d	X													
K-SADS-PL ^e	X													
CY-BOCS ^f	X													
Inclusion/exclusion criteria	X	X												
Demography	X													
Medical history	X													
Psychiatric history	X													
Record current psychotropic therapy ^g	X	X	X	X		X	X	X	X	X	X	X	X	X

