7.4 Primary and Secondary Endpoint Analyses

7.4.1 Primary Endpoint Analysis

The primary endpoint is time from randomization to relapse during the double-blind randomized withdrawal phase. Subjects who complete or discontinue from the randomization phase without relapses will be considered as censored observations. The primary objective of the trial is to evaluate the long-term efficacy of aripiprazole once-daily treatment in pediatric subjects with TD. This will be accomplished by comparing the long-term efficacy of aripiprazole full-dose and half-dose with that of placebo with regard to time to relapse. Hazard ratio and its 95% confidence interval (CI) will be estimated from the Cox proportional hazard model with treatment as a factor. The p-value from the log rank test will be presented to compare survival (subjects free of relapse) distributions, ie, Kaplan-Meier (KM) curves, between the treatment groups.

Analyses of the primary endpoint will use the data of subjects from the ITT Sample.

The statistical comparison will be performed by the log-rank test comparing each aripiprazole treatment groups with placebo at an overall nominal significance level of 0.05 (two-sided) following a group sequential procedure described as follows. One IA is planned at approximately 70% of events accrual time point using the O'Brien-Fleming boundaries for rejection of the null hypothesis, as detailed in [Table 7.4.1-1](#).

Protocol 31-14-204

Table 7.4.1-1 Boundaries for Rejection of Null Hypothesis for Interim and Final Analysis		
Analysis	Number of Events	Two-sides Alpha Level^a
Interim analysis (\approx 70%)	36	0.016
Final analysis (100%)	51	0.045

^aObtained using East 6.4 sample size software.

As there are 2 comparisons of the primary endpoint (one for aripiprazole full-dose vs placebo and the other for aripiprazole half-dose vs placebo), Type I error rate will be controlled for the primary endpoint at the alpha level specified in [Table 7.4.1-1](#) using a fixed sequence procedure in the order of the full-dose and then the half-dose comparisons. That is, one must reject the null hypothesis of the comparison of aripiprazole full-dose to placebo at the level of 0.016 for interim analysis and 0.045 for final analysis (two-sided) in order to proceed to test the hypothesis of the comparison of aripiprazole half-dose to placebo at the level of 0.016 for interim analysis and 0.045 for final analysis (two-sided).

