As a secondary analysis of the primary endpoint, the proportion of subjects experiencing relapse during the double-blind randomized withdrawal phase will be compared between each of the aripiprazole dose groups to placebo. The proportion of relapsed subjects will be computed as 1 minus the KM estimate of the proportions of subjects free of relapses during the double-blind randomized withdrawal phase. Group difference in the proportion of relapsed subjects will be tested using 2-sided Z test with standard error computed from the Greenwood formula. Point estimate of the group difference and its 95% CI will also be provided

Sensitivity analyses will be conducted to assess the sensitivity of the primary efficacy analysis results to the potential informative censoring which will be detailed in the SAP.

Subgroup analyses may be conducted for the primary endpoint based on subject baseline YGTSS TTS score, sex, and age if specific subgroups have reasonable sample sizes to permit such analyses.

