7.4.3.2 Double-blind Randomized Withdrawal Phase

Exploratory efficacy endpoints during the double-blind randomized withdrawal phase include:

- Mean change from randomization to last visit (Week 12 for completers and withdrawal visit for discontinued subject) in YGTSS TTS score
- Mean change from randomization to last visit (Week 12 for completers and withdrawal visit for discontinued subject) in Total YGTSS score
- Mean change from randomization to last visit (Week 12 for completers and withdrawal visit for discontinued subject) in CGI-TS Severity score
- CGI-TS Improvement score at last visit (Week 12 for completers and withdrawal visit for discontinued subject)

For the above endpoints except the CGI-TS Improvement score, randomization baseline is defined as the assessment taken at the last visit of the open-label stabilization phase prior to the first dose of the randomized IMP.

Variables in the form of change from randomization baseline will be analyzed using mixed model repeated measures (MMRM) under the assumption of missing at random (MAR). The time variable is scheduled visits, which will be treated as a categorical repeated factor. The MMRM model will include terms of treatment, visit, and treatment by visit interactions as fixed categorical effects, baseline as well as baseline by visit interactions as covariates, and a single unstructured covariance matrix assumed for all treatment arms in the model. Restricted maximum likelihood estimates of the treatment difference, their 2-sided 95% CIs and p-values (using Kenward-Roger degrees of freedom) from the MMRM inference will be provided.

The change from randomization baseline to Week 12 of the double-blind randomized withdrawal phase in the above variables will also be analyzed using analysis of covariance (ANCOVA) with missing data being imputed by last observation carried

Protocol 31-14-204

forward. The ANCOVA model will include treatment as a factor and baseline value as a covariate.

To evaluate the sensitivity of the results to missing data that are potentially missing not at random (MNAR), sensitivity analyses will be conducted with multiple imputations for missing data under the assumption of MNAR, which will be detailed in the SAP.

CGI-TS Improvement score from postbaseline visits will be analyzed in a similar fashion to those change from baseline variables except that there will not be adjustment for baseline value in the analyses of CGI-TS Improvement score.

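### Randomization is stratified by region and weight group, but no efficacy analysis in Protocol 7.4 uses either factor; stratifying is cheap and gains power only if the factors clearly predict relapse

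*Protocol*

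**What the plan says.** The synopsis (Trial Design) states: "Randomization will be stratified by region and weight group". Protocol 3.6.1 repeats it ("The randomization will be stratified by region and weight group") and defines the levels: North America versus rest of the world, and baseline weight below 50 kg versus 50 kg or more. That makes four strata.

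The analyses then run as follows.

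- **Primary test (7.4.1):** "The statistical comparison will be performed by the log-rank test comparing each aripiprazole treatment groups with placebo". No strata are named.
- **Hazard ratio (7.4.1):** "estimated from the Cox proportional hazard model with treatment as a factor". The interim Cox model in 7.4.4 likewise has treatment only.
- **Relapse proportions (7.4.1):** "Group difference in the proportion of relapsed subjects will be tested using 2-sided Z test with standard error computed from the Greenwood formula". This is a single unstratified comparison per dose.
- **MMRM (7.4.3.2):** "The MMRM model will include terms of treatment, visit, and treatment by visit interactions as fixed categorical effects", plus baseline and baseline by visit.
- **ANCOVA (7.4.3.2):** "The ANCOVA model will include treatment as a factor and baseline value as a covariate".

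The possible subgroup factors in 7.4.1 are baseline tic score, sex and age, so the stratification factors have no part in any planned efficacy analysis. No reason is given.

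The SAP runs none of these tests or models. Because the trial was terminated, SAP 8.1.1 reports only the relapse rate by group, SAP 13 has no interim analysis and SAP 14 makes all efficacy endpoints descriptive.

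**The concern.** Stratified allocation balances the factors across arms. If they predict relapse, that balance makes the treatment contrast less variable than an unstratified test assumes. The test then rejects a true null less often than its nominal level and gives up some power. With 114 subjects and about 38 events in each pairwise comparison, a few points of power are worth having.

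The trade runs the other way if the factors are weak. Splitting few events over four strata loses information, most of all at the interim. Under Protocol 3.8.1 and 7.4.4 the interim is the only look that can stop the trial early for efficacy. So the question is how large the gain and the loss are.

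**Working it through.** **Inputs from the protocol.** 38 subjects per arm, 1:1:1. Relapse 65% on placebo and 34% on each aripiprazole dose. Hazard ratio 0.4. Two-sided alpha 0.016 at 36 events and 0.045 at 51 events (7.1, 7.4.1). Recruitment comes from 3.7: "including an estimated 30-month recruitment period".

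**The plan's own figures.**
- Events over three arms: 38 × (0.65 + 0.34 + 0.34) = 50.5, stated as 51.
- Events in one pair: 38 × (0.65 + 0.34) = 37.6.
- Hazard ratio implied by the rates: ln(0.66)/ln(0.35) = 0.396, stated as 0.4.
- Schoenfeld power at alpha 0.05: Φ(√(37.6/4) × |ln 0.4| − 1.96) = Φ(0.85) = 80.2%.

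The sample size is therefore reproduced without strata.

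**Simulation set-up.** 100,000 three-arm trials per scenario, testing full dose against placebo. Relapse times are exponential over 12 weeks, with marginal rates held at 65% and 34%. Entry is uniform over 30 months. The interim cut is at the 36th relapse over all arms (about 26.5 events in this comparison), and at the final look all 114 are followed to Week 12. Assumptions not in the documents: the stratum effects, stratum sizes per arm (even 10/9/10/9, uneven 16/7/11/4), exact balance over strata, uniform entry, and no dropout. The Monte Carlo standard error of a power difference is 0.06 to 0.10 points.

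**Power (%), unstratified → stratified log-rank, with the difference in points.**

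| Hazard ratios of the two factors | Strata | Interim (0.016) | Final look (0.045) | Either look, difference |
|---|---|---|---|---|
| neither prognostic | even | 46.79 → 44.60 (−2.2) | 79.01 → 78.18 (−0.8) | −0.8 |
| | uneven | 46.42 → 44.24 (−2.2) | 78.69 → 77.83 (−0.9) | −0.9 |
| both 1.25 | even | 46.52 → 44.87 (−1.7) | 78.74 → 78.53 (−0.2) | −0.2 |
| | uneven | 46.75 → 44.73 (−2.0) | 79.02 → 78.55 (−0.5) | −0.5 |
| one 1.5 | even | 46.62 → 45.35 (−1.3) | 79.15 → 79.17 (0.0) | 0.0 |
| | uneven | 46.87 → 45.48 (−1.4) | 79.05 → 78.95 (−0.1) | −0.1 |
| both 1.5 | even | 47.03 → 46.68 (−0.4) | 79.40 → 80.14 (+0.7) | +0.7 |
| | uneven | 46.56 → 45.52 (−1.0) | 79.20 → 79.55 (+0.4) | +0.3 |
| one 2 | even | 47.20 → 47.95 (+0.8) | 79.97 → 81.46 (+1.5) | +1.4 |
| | uneven | 47.22 → 47.54 (+0.3) | 79.70 → 81.08 (+1.4) | +1.4 |
| both 2 | even | 47.55 → 51.60 (+4.1) | 80.79 → 84.20 (+3.4) | +3.3 |
| | uneven | 47.59 → 49.90 (+2.3) | 80.74 → 83.28 (+2.5) | +2.5 |

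**Type I error.** Under the null every arm relapses at 51/114 = 44.7%. At the final look (nominal 4.5%) the unstratified test rejects 4.5–4.6% with no stratum effect, 4.2% with both at 1.5 and 3.6–3.7% with both at 2; repeat simulations of that last case gave 3.3–3.5%. The stratified test rejects 4.5–4.7%. Over both looks (nominal 5%), with both factors at 2, the unstratified test rejects about 4%. The stratified test rejects 5.1–5.3% over the scenarios.

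**Kaplan-Meier Z test.** At nominal 5% under the null, the planned unstratified version rejects about 4–5%. A version combined over strata by size, with Greenwood errors, rejects about 7%: the variance estimate is unreliable in cells of 4 to 16 subjects.

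**ANCOVA.** If the two factors explain a share R² of residual variance, the standard error shrinks by 1 − √(1 − R²) and the unadjusted 5% test has size 2 × (1 − Φ(1.96/√(1 − R²))). For assumed R² of 2%, 5% and 10%, the standard error falls 1.0%, 2.5% and 5.1%, and the unadjusted size is 4.8%, 4.4% and 3.9%.

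**A different set-up.** Here the hazard ratio is held at 0.4 within strata, relapse is found at the scheduled visits, allocation uses permuted blocks, and there is one test at 0.05. With equal strata, blocks of 3 and no dropout, power goes from 79.3% to 78.9% if neither factor matters, from 78.0% to 79.0% with both at 1.5, and from 75.3% to 79.2% with both at 2. Varying stratum shares, block size and dropout (0% or 15%), the changes are −0.4 to −1.0, −0.4 to +1.0 and +1.8 to +4.5 points.

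**The case against.** The strongest reply is that nothing here is wrong. Both tests are valid, the power figure is reproduced, and choosing between them is a preference. Stratifying loses interim power in four of the six scenarios, and over both looks it moves power by less than one point either way unless a factor reaches about 2. The documents offer no evidence that either factor does. And the trial is over: none of these tests will be run.

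Most of this stands, and it sets the weight of the point. It is an efficiency matter with no effect on any reported result, and the interim cost is real.

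Two technical remarks also stand. First, the power levels in the table depend on holding the marginal rates fixed, which makes the within-stratum effect stronger than 0.4 when the factors are prognostic. With 0.4 held within strata, the unstratified test falls to about 75% with both factors at 2. The gain from stratifying is much the same, but agreement with 80% is a statement about the marginal rates. Second, a stratified Cox model estimates a within-stratum hazard ratio, not a marginal one.

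The simulation also follows all 114 subjects and does not apply the rule that stops enrollment at 51 events.

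None of this removes the mismatch. The sponsor chose these two factors for allocation, and the plan does not say why the analysis ignores them.

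**Conclusion.** The point holds as an optional improvement to the protocol's plan. The omission makes the planned tests somewhat conservative if region or weight group predicts relapse; it does not make them invalid. Over both looks, stratifying the log-rank test changes power by between −0.9 points (neither factor prognostic) and +3.3 points (both at hazard ratio 2). At the interim alone the range is −2.2 to +4.1 points. The prognostic strengths are assumptions, so which end applies cannot be settled from the documents. For the MMRM and ANCOVA, two extra fixed effects cost almost nothing.

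**What to change.** - **Protocol 7.4.1 and 7.4.4:** stratify the log-rank test and the Cox model by region and baseline weight group as recorded in the IRT. Use the same statistic at both looks and do not pool strata after seeing the data; a stratum with no events simply contributes nothing. Describe the hazard ratio as within-stratum.
- **Protocol 7.4.1, Kaplan-Meier Z test:** leave it unstratified and label it an unstratified supportive analysis, since combining it over strata this small rejects about 7% under the null.
- **Protocol 7.4.3.2:** add region and baseline weight group as fixed effects in the MMRM and ANCOVA.
- **SAP:** no change.

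The cost is one phrase per analysis and no new data. The downside with weak factors (no effect, both at 1.25, or one at 1.5) is 1.3 to 2.2 points of power at the interim and up to about 0.9 points over both looks. With both at 1.5, an interim cost of about 0.4 to 1.0 points remains.

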7.4.2 Secondary Endpoint Analysis

Not applicable.

Protocol 31-14-204

7.4.3 Exploratory Efficacy Endpoint Analysis

7.4.3.1 Open-label Stabilization Phase

Descriptive statistics will be provided for the scores of each efficacy scale assessed during the open-label stabilization phase and their change from trial baseline for the Open-label Safety Sample. For CGI-TS Improvement score, only its observed value at each visit will be summarized.

7.4.3.2 Double-blind Randomized Withdrawal Phase

Exploratory efficacy endpoints during the double-blind randomized withdrawal phase include:

- Mean change from randomization to last visit (Week 12 for completers and withdrawal visit for discontinued subject) in YGTSS TTS score
- Mean change from randomization to last visit (Week 12 for completers and withdrawal visit for discontinued subject) in Total YGTSS score
- Mean change from randomization to last visit (Week 12 for completers and withdrawal visit for discontinued subject) in CGI-TS Severity score
- CGI-TS Improvement score at last visit (Week 12 for completers and withdrawal visit for discontinued subject)

For the above endpoints except the CGI-TS Improvement score, randomization baseline is defined as the assessment taken at the last visit of the open-label stabilization phase prior to the first dose of the randomized IMP.

Variables in the form of change from randomization baseline will be analyzed using mixed model repeated measures (MMRM) under the assumption of missing at random (MAR). The time variable is scheduled visits, which will be treated as a categorical repeated factor. The MMRM model will include terms of treatment, visit, and treatment by visit interactions as fixed categorical effects, baseline as well as baseline by visit interactions as covariates, and a single unstructured covariance matrix assumed for all treatment arms in the model. Restricted maximum likelihood estimates of the treatment difference, their 2-sided 95% CIs and p-values (using Kenward-Roger degrees of freedom) from the MMRM inference will be provided.

The change from randomization baseline to Week 12 of the double-blind randomized withdrawal phase in the above variables will also be analyzed using analysis of covariance (ANCOVA) with missing data being imputed by last observation carried

Protocol 31-14-204

forward. The ANCOVA model will include treatment as a factor and baseline value as a covariate.

To evaluate the sensitivity of the results to missing data that are potentially missing not at random (MNAR), sensitivity analyses will be conducted with multiple imputations for missing data under the assumption of MNAR, which will be detailed in the SAP.

CGI-TS Improvement score from postbaseline visits will be analyzed in a similar fashion to those change from baseline variables except that there will not be adjustment for baseline value in the analyses of CGI-TS Improvement score.

